## 5.3 Study Population

Eligible vaccinated individuals for the primary analysis are persons who received a bivalent booster and met the following inclusion/exclusion criteria regardless of the occurrence of the stroke outcomes. All eligible vaccinated individuals will be used for the attributable risk (AR) calculation

The case population will consist of bivalent booster vaccinated individuals with a stroke outcome. Incident stroke outcomes will be defined as the first recorded outcome for an individual during the study observation period if there are no claims for the same stroke outcomes in the preceding pre-defined clean window. The clean window will be anchored on the date of the stroke outcomes and will begin a pre-defined number of days prior to the stroke outcomes as specified in Section 4.3.

Eligible vaccinated individuals should meet the following inclusion/exclusion criteria.

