### 4.3 Outcomes

The stroke outcomes included in the study are hemorrhagic stroke (HS), non-hemorrhagic/ischemic stroke (NHS), transient ischemic attack (TIA), and a combined outcome which includes persons who have been diagnosed with non-hemorrhagic stroke and/or TIA (NHS/TIA). Risk following bivalent booster vaccination will be assessed separately for each of these stroke outcomes by vaccine brand. Stroke outcomes will be identified with International Classification of Diseases, Tenth Revision, Clinical Modification (ICD-10-CM) codes in either primary or secondary diagnosis positions.

The ICD-10 codes used to identify each stroke outcome, the care settings in which each outcome will be evaluated, as well as the clean and risk windows for each are described in Table 4. The first qualifying occurrence of the outcome in the observation period is defined as an incident stroke outcome only if no outcome of the same type was recorded during the preceding pre-defined clean window. The clean window is defined as a period prior to vaccination in which beneficiaries with an occurrence of an event during the pre-specified window are excluded because outcomes captured post-vaccination may be attributed to previous rather than incident risk. The risk window is defined as an interval post-vaccination during which occurrence of the stroke outcomes may be associated with the vaccine exposure and thus considered a qualifying outcome. Both clean and risk windows are selected based on literature review, consultation with subject matter experts, and to align with CDC definitions. Risk windows are further detailed in Section 5.4.2.

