#### **Exclusion Criteria**

- I. Individuals less than 65 years of age at the time of bivalent booster vaccination.
- II. Individuals vaccinated with multiple brands on the same day or multiple vaccinations (same/different brand) within 3 days of each other
- III. Individuals who had a dialysis claim (identified as a type of bill code 72x) in the 90 days prior to event; excluded as we expect these patients to have a greater mortality risk than the typical Medicare beneficiary
- IV. Individuals on hospice care on vaccination date; excluded because high fatality rate amongst this group may violate SCCS methods assumptions.
- V. Individuals who reside in a nursing home at any point between August 31, 2022 and vaccination date.
- VI. For case population only:
  - a. Individuals that do not contribute follow-up time to both risk and control intervals. If individuals disenroll or reach the end of the study period during the risk window prior to accumulating any time for post-vaccination control intervals, they will be excluded.

- b. Individuals who had a diagnosis of a stroke outcome during the outcome-specific clean window.
- c. Individuals who had a diagnosis of COVID-19 in the 30 days prior to the stroke outcome.
- d. Individuals who reside in a nursing home at any point between vaccination date and outcome date.

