#### **Exclusion Criteria**

- I. Individuals less than 65 years of age at the time of influenza vaccination.
- II. Individuals vaccinated with multiple brands of an influenza vaccine on the same day or multiple vaccinations (same/different brand) within 3 days of each other
- III. Individuals who receive a concomitant bivalent booster vaccination
- IV. Individuals who had a dialysis claim (identified as a type of bill code 72x) in the 90 days prior to vaccination; excluded as we expect these patients to have a greater mortality risk than the typical Medicare beneficiary
- V. Individuals on hospice care on vaccination date; excluded because high fatality rate amongst this group may violate SCCS methods assumptions.
- VI. Individuals who reside in a nursing home at any point between August 31, 2022 and vaccination date.
- VII. For case population only:
  - a. Individuals that do not contribute follow-up time to both risk and control intervals. If individuals disenroll or reach the end of the study period during the risk window prior to accumulating any time for post-vaccination control intervals, they will be excluded.

- b. Individuals who had a diagnosis of a stroke outcome during the outcome-specific clean window.
- c. Individuals who had a diagnosis of COVID-19 in the 30 days prior to the stroke outcome.
- d. Individuals who reside in a nursing home at any point between vaccination date and outcome date.

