#### 5.5.2.2 Attributable Risk (AR) Estimate

The study will also estimate the AR (per 100,000 doses and person-years). The number of excess stroke cases due to the vaccine will be directly derived from the conditional Poisson regression model, defined as the difference between the sum of the model fitted values (i.e., model predicted number of cases), and the sum of the expected cases if there were no vaccinations (i.e., all observed time is treated as control time). The AR is the excess number of stroke outcomes cases divided by the number of eligible beneficiaries (or eligible follow up dose-years). The standard error (SE) of the AR is estimated by bootstrap resampling 10,000 times. For each iteration, the study will sample the beneficiaries with stroke outcomes with replacement and repeat the AR calculation. The SE is calculated as the square root of the variance of the 10,000 AR values.

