## A Appendix

**Table A. ICD-10 Codes Which Indicate Onset Date Adjustment or Exclusion for Outcomes of Interest**

Outcome	Adjust onset date if observed in the 1 day prior to outcome (in all settings)	Exclusions for Prevalence (in all settings)	Exclusions – other known causes (in all settings)
Hemorrhagic Stroke (HS)	I63.9, R51*, R47*, R29.810, R53.1, R42*, R41.82, R40.4, H53.13*, H53.9, G81.9*	If occurs in the 365 window prior to outcome I69*, Z86.73	If in last 30 days prior to outcome U07.1 If in last 1 day prior to outcome S06* If same day as outcome S06*, Physical Trauma Code
Non-Hemorrhagic Stroke (NHS)	Z92.82, R51*, R47*, R29.810, R53.1, R42, R41.82, R40.4, G81.9*, H53.9, H53.13*	If occurs in the 365 window prior to outcome I69*, Z86.73, I48*, D57*, D68.5*	If in last 30 days prior to outcome U07.1 If in last 28 days prior to outcome I21* If in last 1 day prior to outcome S15*, 174* In same day as outcome S15*, I74*, Physical Trauma Code

Outcome	Adjust onset date if observed in the 1 day prior to outcome (in all settings)	Exclusions for Prevalence (in all settings)	Exclusions – other known causes (in all settings)
Non-hemorrhagic stroke or Transient Ischemic Attacks (NHS / TIA)	Z92.82, R51*, R47*, R29.810, R53.1, R42, R41.82, R40.4, G81.9*, H53.9, H53.13*	If occurs in the 365 window prior to outcome I69*, Z86.73, I48*, D57*, D68.5*	If in last 30 days prior to outcome U07.1 If in last 28 days prior to outcome I21* If in last 1 day prior to outcome S15*, I74* In same day as outcome S15*, I74*, Physical Trauma Code
Transient Ischemic Attacks (TIA)	R51*, R47*, R29.810, R53.1, R42, R41.82, R40.4, G81.9*, H53.9, H53.13*	If occurs in the 365 window prior to outcome I69*, Z86.73, I48*, D57*, D68.5*	If in last 30 days prior to outcome U07.1 If in last 28 days prior to outcome I21* If in last 1 day prior to outcome S15* In same day as outcome S15*, Physical Trauma Code

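### The attributable risk divides cases filtered by case-only exclusions by vaccinees who are not so filtered, which pulls it toward zero; the dialysis and clean-window anchors also need reconciling

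*Protocol*

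**What the plan says.** **Denominator.** Section 5.3 defines eligible vaccinees as booster recipients who "met the following inclusion/exclusion criteria regardless of the occurrence of the stroke outcomes", and adds: "All eligible vaccinated individuals will be used for the attributable risk (AR) calculation". Section 5.5.2.2 gives the formula: "The AR is the excess number of stroke outcomes cases divided by the number of eligible beneficiaries", with follow-up dose-years as the alternative divisor.

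**Numerator.** The excess comes from the conditional Poisson model, which is fitted to cases. Section 5.3.1, item VI, lists four exclusions for cases alone:
- (a) no follow-up in both risk and control time
- (b) a stroke outcome in the clean window
- (c) COVID-19 in the 30 days before the stroke
- (d) nursing-home residence between vaccination and outcome

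Section 4.3 also removes cases that carry the codes in Appendix Table A. The prevalence codes there apply under the rule "If occurs in the 365 window prior to outcome". They are I69* and Z86.73 for HS; NHS, TIA and NHS/TIA add I48*, D57* and D68.5*.

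**Dialysis.** Section 5.3.1, item III, sits outside the case-only list and excludes "Individuals who had a dialysis claim (identified as a type of bill code 72x) in the 90 days prior to event". Section 5.3.2, item IV, for the influenza analysis, excludes "Individuals who had a dialysis claim (identified as a type of bill code 72x) in the 90 days prior to vaccination".

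**Clean window.** Section 4.3 says: "The clean window is defined as a period prior to vaccination in which beneficiaries with an occurrence of an event". Section 5.3 says: "The clean window will be anchored on the date of the stroke outcomes", and the note to Table 4 also uses the outcome date.

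**The concern.** A risk per dose needs a numerator and a denominator drawn from the same people. Here a vaccinee with, say, an I48* code in the look-back year cannot become a counted NHS case, yet still adds a dose and dose-time to the divisor. The same holds for a vaccinee whose enrolment or study period ends before control time begins. The AR then describes neither the analysed population nor, unless the removed cases carry no vaccine effect, all vaccinees.

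The anchors raise a second and separate difficulty. Eligibility is meant to be settled whether or not a stroke occurs, but the primary dialysis rule needs an event date, which non-cases lack. Two programmers could build different denominators, and the bivalent and influenza ARs would rest on different dialysis rules. The clean-window conflict leaves open which people count as cases.

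**Working it through.** The protocol states no AR, case count or number of doses, so there is no figure to reproduce. The check is algebraic, with assumed inputs.

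**Inputs**
- N: eligible vaccinees, the divisor in Sections 5.3 and 5.5.2.2.
- q: share of vaccinees (or dose-time) who would fail a case-only or Table A exclusion. Not given; assumed 1% to 30%.
- b: baseline events per dose over the risk window in the retained group. Not given; assumed 20 per 100,000 for illustration.
- IRR: not given; assumed 0.9, 1.0 and 1.2.
- r: baseline stroke rate in the excluded group relative to the retained group. Not given; assumed 2 and 4.

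**Step 1: same exclusions above and below the line.** Retained excess E = N(1-q) × b × (IRR-1).
- Written AR = E/N
- Matched AR = E/[N(1-q)]
- Written/matched = 1-q, for any IRR other than 1

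With b = 20 per 100,000 and q = 20%:

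| IRR | Matched AR = 20 × (IRR-1) | Written AR = 0.8 × matched |
|---|---|---|
| 1.2 | 4.0 per 100,000 | 3.2 per 100,000 |
| 1.0 | 0 | 0 |
| 0.9 | -2.0 per 100,000 | -1.6 per 100,000 |

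The effect is therefore attenuation toward zero. The ratio is 0.99, 0.95, 0.90, 0.80 and 0.70 for q = 1%, 5%, 10%, 20% and 30%.

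**Step 2: compared with an AR for all vaccinees.** If the excluded group has the same IRR, written/all = (1-q)/[(1-q) + q × r].
- r = 2, q = 10%: 0.90/(0.90 + 0.20) = 0.82
- r = 2, q = 20%: 0.80/(0.80 + 0.40) = 0.67
- r = 4, q = 20%: 0.80/(0.80 + 0.80) = 0.50

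If the excluded cases carry no vaccine excess at all, the ratio is 1.00 and there is no distortion on this reading.

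**Step 3: precision.** The bootstrap in Section 5.5.2.2 resamples cases and repeats the same division. The standard error shrinks by the same factor 1-q, and the interval gives no sign of the shift.

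**Step 4: anchors side by side**

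| Rule | Anchor | Place |
|---|---|---|
| Clean window | Vaccination | Section 4.3 text |
| Clean window | Outcome | Table 4 note; Section 5.3 |
| Dialysis, primary analysis | Event | Section 5.3.1, item III |
| Dialysis, influenza analysis | Vaccination | Section 5.3.2, item IV |

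The clean window conflicts with itself between sections. The dialysis rule differs between two analyses and, in the primary one, cannot be evaluated for non-cases.

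**The case against.** The strongest defence is that the written AR is a definable quantity: excess qualifying cases per eligible dose. Section 4.3 explains the Table A exclusions as removing strokes that probably have causes other than the vaccine. If those strokes carry no vaccine excess, dividing by all vaccinees is correct (Step 2, ratio 1.00). This stands in part. But the protocol does not label the AR that way; Section 5.5.2.2 presents the numerator as the excess due to the vaccine. Table A also keeps its prevalence codes in a separate column from other known causes. For people with those histories, a vaccine excess is unmeasured rather than shown to be absent.

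Further points for the sponsor stand. The hypotheses concern the IRR, which the denominator does not touch, and the AR is an additional estimate. With dose-years as divisor, short follow-up already carries less weight. The Table A exclusions follow the CDC's algorithm, which is a reason to retain them for the IRR.

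Some stronger readings are not supported:
- A reader might infer that the AR is always understated. That is so only when the IRR exceeds 1.
- A reader might infer that the clean-window and dialysis anchors contradict one another. In the primary analysis, Table 4, Section 5.3 and item III tie both to the outcome or event.
- A reader might infer that the anchor conflicts cause the attenuation. The case-only filtering does; the anchors only make eligibility ambiguous.
- A reader might infer that an outcome-anchored clean window, sliding with the event date, lowers the IRR by a known amount. The protocol gives no incidence or recurrence figure from which to size this. Table A's I69* and Z86.73 rules would remove many of the prior-stroke patients concerned. Nor does re-entry occur only in control time: a stroke 360 days before vaccination clears a 365-day window around day 6, inside the first risk window, and strokes about 323-344 days before clear it during days 22-42.

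**Conclusion.** The point holds for the AR only. As written, the AR equals (1-q) times the AR with a matched denominator: attenuated when the IRR differs from 1 and unchanged when it equals 1. An assumed q of 5-20% gives an AR 5-20% too small, for example 3.2 instead of 4.0 per 100,000 at q = 20% under the inputs above. The true size cannot be fixed from the protocol, because q is not given and one value cannot serve every outcome: I48*, D57* and D68.5* do not apply to HS.

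Two wording conflicts hold independently of that arithmetic. The primary dialysis rule cannot be applied to non-cases and differs from the influenza rule, and the clean window has two anchors. Neither implies a bias of known direction, but together they mean that neither the AR denominator nor the case set can be built in only one way.

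**What to change.** 1. **Clean window.** Bring Section 4.3, the Table 4 note and Section 5.3 to one anchor.
2. **Dialysis.** Use one anchor in both analyses that can be evaluated for non-cases, such as the vaccination date already used in Section 5.3.2.
3. **History exclusions for the AR.** Apply the prior same-type stroke rule and the Table A prevalence codes, looking back 365 days from vaccination, to vaccinees and cases alike, and take the excess from the model fitted to that case set. Section 5.3.1, item II, already requires 365 days of enrolment before vaccination, so the data are there.
4. **Follow-up.** Leave out of the AR denominator doses whose enrolment or study period ends before control time begins. In the dose-year version, end dose-time at post-vaccination nursing-home entry and remove the 30 days after a COVID-19 diagnosis, to mirror items VI.c and VI.d.
5. **Label.** If the all-vaccinee denominator is kept, report that AR as excess qualifying cases per 100,000 doses given, beside the matched AR.

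The outcome-anchored history rules may stay for the IRR, or as a sensitivity analysis aligned with the CDC. The cost is revised wording, a cohort re-run, and a somewhat larger AR if the IRR exceeds 1.

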### 5.3.1 Primary Analysis: Beneficiaries 65 years and older

#### **Inclusion Criteria**

- I. Medicare beneficiaries enrolled in Part A (hospital insurance) and Part B (medical insurance) during the study observation period
- II. Continuous enrollment will be required from 365 days prior to vaccination date until the earlier of 90 days post-vaccination, disenrollment, administration of a subsequent mRNA COVID-19 vaccine, death or study period end.
- III. Received a bivalent booster in the observation period but not before the bivalent booster EUA, August 31, 2022.
- IV. For case population only, had a record of a stroke outcome diagnosis during the study observation period.

#### **Exclusion Criteria**

- I. Individuals less than 65 years of age at the time of bivalent booster vaccination.
- II. Individuals vaccinated with multiple brands on the same day or multiple vaccinations (same/different brand) within 3 days of each other
- III. Individuals who had a dialysis claim (identified as a type of bill code 72x) in the 90 days prior to event; excluded as we expect these patients to have a greater mortality risk than the typical Medicare beneficiary
- IV. Individuals on hospice care on vaccination date; excluded because high fatality rate amongst this group may violate SCCS methods assumptions.
- V. Individuals who reside in a nursing home at any point between August 31, 2022 and vaccination date.
- VI. For case population only:
  - a. Individuals that do not contribute follow-up time to both risk and control intervals. If individuals disenroll or reach the end of the study period during the risk window prior to accumulating any time for post-vaccination control intervals, they will be excluded.

- b. Individuals who had a diagnosis of a stroke outcome during the outcome-specific clean window.
- c. Individuals who had a diagnosis of COVID-19 in the 30 days prior to the stroke outcome.
- d. Individuals who reside in a nursing home at any point between vaccination date and outcome date.

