**Table 4. Stroke outcomes and their respective care settings, clean and risk windows**

Stroke outcomes	ICD-10 Codes	Care Setting (Primary and Secondary Analysis)	Clean Window	Risk Window
Hemorrhagic stroke (HS)	I61*, I62*	IP	365 days	1-21 days; 22-42 days
Non-hemorrhagic stroke (NHS)	I63*	IP	365 days	1-21 days; 22-42 days
Transient ischemic attack (TIA)	G45.8, G45.9	IP; OP-ED	365 days	1-21 days; 22-42 days
Non-hemorrhagic stroke or transient ischemic attack (NHS/TIA)	I63*, G45.8, G45.9	IP (NHS & TIA); OP-ED (TIA)	365 days	1-21 days; 22-42 days

Definitions: Clean Window is defined as an interval relative to stroke outcomes date used to define incident stroke outcomes where an individual enters the study cohort only if the stroke outcomes of interest did not occur during that interval. Risk Window is defined as an interval relative to exposure date during which occurrence of the stroke outcomes of interest will be included in the analyses

Follow-Up Analysis II – Care Settings will include the OP-ED setting for all outcomes.

If certain related outcome codes are observed in the one day prior to the stroke outcome of interest, we will adjust the onset date of the stroke outcome to start at the date of the related outcome. If certain outcome codes which may be associated with the onset of the stroke outcome are observed prior to or on the day of the stroke outcome, these cases will be excluded. These exclusions are implemented to clean the outcome cohort by eliminating stroke cases which are likely caused by factors other than vaccination. These exclusions are implemented in the CDC VSD Rapid Cycle Analysis (RCA). The Appendix details these adjustments/exclusions (See Appendix Table A).

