### 5.4.1 Observation Period/Follow-Up

For each individual, the observation period will start from the day following bivalent booster vaccination date, i.e., day 1 after vaccination and until the earlier of 90 days post-vaccination, disenrollment, administration of a subsequent mRNA COVID-19 vaccine, death or study period end. Day 0 (date of vaccination) is not included in the observation period since we would not be able to attribute stroke outcomes on this day to the exposure.

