### 5.4.2 Risk Window

The risk interval is defined as the time during which risk of a stroke outcome is hypothesized to be related to vaccination based on biological plausibility and clinical input (Table 2). The selected risk intervals for all stroke outcomes are days 1-21 and days 22-42. The 1-21 day risk interval was selected to align with the definition of stroke as used by the CDC in their RCA. The 22-42 day risk interval is selected to assess any difference in risk during this period, and to avoid any biases in risk estimates that may arise from a carryover effect from the vaccine exposure into the control interval. Implementing a split window addresses concerns that risk of the outcomes may not be constant throughout the risk period. Risk intervals will not be split further in an effort to preserve statistical power.

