### 5.4.3 Control Window

The post-vaccination control interval is defined as all follow-up time during the observation period following a vaccination that is outside of the risk interval(s) until the earlier of 90 days post-vaccination, disenrollment, subsequent mRNA COVID-19 vaccination, death, or study period end. Individuals who only accrued data during the risk intervals will be excluded from the analysis.

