## 5.5.2 Primary Analysis: SCCS with Post-vaccination Control Intervals

### 5.5.2.1 Incidence Rate Ratio (IRR) Estimation

For the primary SCCS analysis, the rates of the stroke outcomes following the bivalent booster doses dose will be evaluated by brand. This analysis will compare the stroke outcomes rates in the risk and control intervals using a conditional Poisson regression model. A Farrington-adjusted SCCS model will be implemented that adjusts for the reduced observation time that can occur from the occurrence of an outcome. We assume that only one incident event can occur in the observation period. Therefore, we only consider the first observed outcome.

$$\log(E(Y|X)) = \beta_1(\text{risk window}_1) + \beta_2(\text{risk window}_2) + \log(t) + \text{strata}(\text{pateint id})$$

$Y = \text{Stroke Outcome}$

$\text{risk interval} = \text{indicator for exposure}$

$t = \text{interval}$

$\text{patient id} = \text{term identifying the patient}$

Under this model, the null and alternative hypotheses for each risk window can be written as, respectively:

$$H_0: e^{\beta_1} = 1 \quad H_a: e^{\beta_1} \neq 1$$

$$H_0: e^{\beta_2} = 1 \quad H_a: e^{\beta_2} \neq 1$$

Where,  $e^{\beta_1}$  and  $e^{\beta_2}$  will be interpreted as the IRR for the stroke outcomes in the risk intervals compared to the control intervals. Thus, statistical significance of the coefficient on the risk interval variable at a pre-specified level will indicate a statistically significant association between COVID-19 vaccination and the stroke outcomes. Statistical significance will be determined using 95% CIs of IRRs and two-sided p-values ( $p \leq 0.05$ ).

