##### 5.5.4.1 Seasonality Adjustment Analysis

To evaluate potential time-varying confounding given the length of the observation period, the study will assess the association of time-varying risk factors with the stroke outcomes and adjust for the changing risk of the stroke outcomes, namely that some of the stroke outcomes exhibit seasonal trends. In addition, given that COVID-19 has been associated with stroke, and the risk of exposure to COVID-19 varies throughout the study period, the risk of related stroke may vary during the study period as well. Baseline stroke outcome risk will be estimated from a similar population during the same calendar months in previous years and will be included as an offset term in the Poisson regression model. For each stroke outcome, rates between 2017-2021 will be evaluated to determine a reasonable comparator year. If rates vary across years, the selected comparator year will be the one with the minimum stroke outcomes rate, whereas if there is limited variation, the median year among 2017-2021 will be selected.

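### Dropping strokes within 30 days after COVID-19 while retained cases keep their post-COVID days shifts the IRR, in a direction the protocol cannot settle

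*Protocol*

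**What the plan says.** Section 5.3.1, exclusion VI.c, applies to cases only and drops "Individuals who had a diagnosis of COVID-19 in the 30 days prior to the stroke outcome". Sections 5.3.2 (VII.c) and 5.3.3 (III.c) repeat it. Appendix Table A lists U07.1 for every outcome under the condition "If in last 30 days prior to outcome". Section 4.3 gives the reason for the Table A exclusions: "These exclusions are implemented to clean the outcome cohort by eliminating stroke cases which are likely caused by factors other than vaccination".

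Time at risk is handled separately. Under 5.4.1 each person is observed from day 1 "until the earlier of 90 days post-vaccination, disenrollment, administration of a subsequent mRNA COVID-19 vaccine, death or study period end". A COVID-19 diagnosis does not end or interrupt that time. Section 5.4.2 states: "The selected risk intervals for all stroke outcomes are days 1-21 and days 22-42". Under 5.4.3 the remaining follow-up is control time, which is days 43-90 for a fully observed case. The model in 5.5.2.1 has two window terms, a log-time offset and a patient stratum, and no COVID-19 term.

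Section 5.5.4.1 notes that "the risk of exposure to COVID-19 varies throughout the study period". It answers this, in a sensitivity analysis, with a baseline-rate offset taken from one comparator year between 2017 and 2021.

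**The concern.** A rule that makes some days ineligible for an event should also take those days out of the time in which an event could occur. Here only the events go. A dropped case takes its own person-time with it, so the mismatch lies in the retained cases: a case with COVID-19 on day 50 and a stroke on day 10 still contributes days 50 to 80 as ordinary control time.

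This is harmless only if post-COVID days form the same share of each window. The protocol itself says COVID-19 exposure varies. The look-back also differs by window: for strokes on days 1-21 part of it falls before vaccination, while for strokes on days 43-90 it falls wholly after. The study exists to resolve a safety signal and judges significance at p ≤ 0.05, so a systematic shift of a few percent can matter if case counts are large. The attributable risk in 5.5.2.2 comes from the same fitted model and inherits the shift.

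**Working it through.** **The plan's nearest figure.** The protocol gives no figure for this exclusion. Section 5.2 does the same kind of calculation for claims delay: 100%/90% − 1 = 11.1%, which reproduces its 11%. Unequal capture of events multiplies the IRR by the ratio of the capture proportions.

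**Formula.** With true IRR 1, expected IRR = (1 − p_risk)/(1 − p_control). For each day, p is 1 − exp(−sum of daily COVID-19 diagnosis rates over the 30 days up to that day), averaged over the window.

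**Inputs.** From the protocol: windows 1-21, 22-42 and 43-90, and the 30-day look-back. Assumed, because the protocol gives none: weekly diagnosed incidence of 0.1%, 0.5% or 1%, and its pattern over time.

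**Worked case.** At 0.5% a week with flat incidence, 30 × 0.005/7 = 0.0214, so p = 2.12% in every window and the ratio is 1. If nobody is diagnosed in the 30 days before vaccination, days 1-21 have on average (1 + … + 21)/21 = 11 look-back days that can hold a diagnosis. Then p_risk = 0.78%, p_control = 2.12%, and 0.9922/0.9788 = 1.014.

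| Assumed pattern | p_risk, p_control at 0.5%/week | Days 1-21 shift at 0.1% / 0.5% / 1% |
|---|---|---|
| Flat | 2.12%, 2.12% | 0 / 0 / 0 |
| None in 30 days before vaccination, then flat | 0.78%, 2.12% | +0.3 / +1.4 / +2.8% |
| Doubling from day −29 to day 90 | 2.57%, 3.53% | +0.2 / +1.0 / +2.0% |
| Tripling, and none before vaccination | 1.26%, 4.91% | +0.8 / +3.8 / +7.9% |
| Falling by half | 1.90%, 1.41% | −0.1 / −0.5 / −1.0% |
| Booster halves incidence from day 14 | 2.07%, 1.07% | −0.2 / −1.0 / −2.0% |
| None before vaccination, and booster halves incidence | 0.73%, 1.07% | +0.1 / +0.3 / +0.7% |

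For days 22-42 the shift runs from −0.9% to +2.9%. Matching the 11% of section 5.2 would need about 10 percentage points more post-COVID time in the control window than in the risk window.

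**Simulation check.** A null case-only model (about 0.9 million cases per scenario, simulation SE about 0.003, COVID-19 stroke rate ratio assumed to be 5) was run with no diagnoses before vaccination. As planned, the days 1-21 IRR was 1.014 at 0.5% a week and 1.023 at 1%. Removing the matching post-COVID time as well gave 1.001 and 0.998.

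**Effect on the test.** Take a null IRR of 1.028, with N cases in one brand-by-outcome analysis (N assumed) and SE = √(1/(21N/90) + 1/(48N/90)). At N = 2,000 the SE is 0.0555 and the two-sided 5% test rejects about 8% of the time. At N = 10,000 the SE is 0.0248 and it rejects about 20% of the time.

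**With no COVID-19 exclusion.** If COVID-19 multiplies the stroke rate by k, the null IRR is (1 + (k − 1)p_risk)/(1 + (k − 1)p_control). For k > 1 this lies on the other side of 1 from the planned analysis. In the worked case with k = 5 it is 1.0312/1.0848 = 0.951, against 1.014 as planned. The gap between the two IRRs is therefore at least as large as the COVID-related bias in the planned one.

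**With matching time removed.** A diagnosis made after the stroke removes later days and never earlier ones, so it costs control time more than days 1-21. In a null simulation (0.5% a week, none before vaccination, 17% 30-day fatality from Table 5), the days 1-21 IRR became about 0.989, 0.980 or 0.963 when 3%, 5% or 10% of cases (assumed) gained a diagnosis in the 14 days after the stroke. With flat incidence the planned analysis gave 1.000, and removing the time gave 0.990, 0.982 or 0.964.

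**The case against.** The exclusion is deliberate: section 4.3 gives a reason for it and says it follows the CDC surveillance definitions. It also removes a bias from COVID-triggered strokes that would generally be larger and of opposite sign (−4.9% against +1.4% in the worked case with k = 5). That stands, and it is why VI.c should stay. A reader might infer that the criterion itself is wrong; the documents do not support that.

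The effect is small, and section 5.2 already accepts up to 11% from claims delay. The size comparison stands. But 5.2 states and argues for its bias, whereas this one goes unmentioned, and the two multiply when control-window capture is the lower in both.

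A reader might also infer that the IRR is probably inflated, because people recently ill put off a booster and control time falls in winter. The documents support neither step: they say only that COVID-19 exposure varies, and give no incidence and no direction. Flat or falling incidence, or protection by the booster, gives zero or negative bias.

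The obvious cure, removing post-COVID time from the primary analysis, is open to challenge too. Testing or infection around a stroke admission makes observation time depend on the outcome, against assumption II in section 5.1. That also stands.

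The existing adjustments do not help. The seasonal offset models historical stroke rates, not which current cases were deleted. The Farrington adjustment concerns follow-up shortened by the outcome.

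**Conclusion.** The mismatch between deleted events and retained time is in the current text, and nothing in the protocol corrects it. Its sign is unknown. Its size rests on assumed incidence: about −2% to +3% for days 1-21 in most patterns at 0.1% to 1% a week, and up to about +8% when tripling incidence is combined with no diagnoses before vaccination. The rejection rates also rest on assumed case counts. This is a modest, unacknowledged bias that the study can examine with its own data. It does not show that the IRR will be inflated, or that the primary case definition should change.

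**What to change.** Keep VI.c in the primary analysis. Add two sensitivity analyses to 5.5.4 for each brand and outcome:

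1. **No COVID-19 exclusion.** Omit VI.c and the U07.1 rule in Table A. If COVID-19 raises stroke risk, as 5.5.4.1 suggests, the two IRRs bracket the COVID-related bias, and agreement within sampling error shows it is negligible. Present this as a contrast, not as a better estimate, because it readmits COVID-triggered strokes.
2. **Matching time removed.** Keep VI.c and also remove the 30 days after any COVID-19 diagnosis from every case's risk and control time, so that log(t) covers only days on which a stroke could count. Label it sensitivity only, and state that diagnoses at or after stroke admission can push the IRR down by about 1% to 4% if 3% to 10% of cases (assumed) gain one.

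Apply both to the influenza and nursing-home analyses. The cost is a little more programming and reporting, using COVID-19 claims the study already needs for VI.c.
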